### **6.13.9 Biomarker and DNA samples**

Samples for genetic (DNA) research and biomarkers may be taken from subjects who provide separate informed consent for these samples to be collected and for their samples to be stored for other research studies. This data will not be reported in this study.

### **6.13.10 Exploratory Bayesian Analyses**

The MFM 32, continuous respiratory measures and continuous strength measures (in absolute values) will also be analyzed in an exploratory manner using Bayesian statistical modeling. Bayesian methods are used as they allow for an easy construction of the predictive distributions. These distributions will be used to assess whether deviations from the natural course of the disease as observed from the run-in and the natural history data are observed after administration of the IMP.

A hierarchical model will be fitted to each of the responses using Bayesian methods. Only non-informative priors will be considered. The data used for the modeling consist of the NHS data or the run-in for patients who did not participate in the NHS. This hierarchical model will contain a random slope and intercept for each subject. The other covariates of the model will be time in months and treatment group. The baseline is at time 0. These models will be performed for each mutation separately.

Using the posterior distributions of the different parameters of the model fitted using NHS or run-in data only, the predictive distributions at future time points of interest in the current study will be generated. Then the predictive probability that an observation would have occurred given the natural course of each patient's disease will be computed. This predictive probability under the assumption of the natural evolution of the disease will also be considered as an additional endpoint or transformation of the clinical endpoint to evaluate the potential effect of the IMP.

The appropriate distribution or transformation to be applied on the observed endpoints will be justified to reflect the nature of the data. For example, the Beta distribution may be used for bounded scales or a logistic transformation for percentages.

These assessments will only be realized at the end of the study and will not be conducted for IDMC purposes.

These Analyses will be conducted by PharmaLex Belgium using SAS v9.4. Bayesian estimations will be realized with the proc MCMC procedure.

## **6.14 Safety Analyses**

The safety analyses (AE, clinical laboratory tests, physical examination, vital signs and ECG) will be presented by the treatment received for the Safety Analysis Set.

### **6.14.1 Adverse Events**

Adverse events will be reported separately for SAD and MAD + MAD Extension parts.

A pre-therapy AE is defined as any AE that starts before the first dose of study drug.

A treatment emergent adverse event (TEAE) is defined as:

- Any AE that has an onset on or after the first dose of study drug and before last dose of study drug + 28 days.
- Any pre-existing AE that has worsened in severity on or after the first dose of study drug and before the last dose of study drug + 28 days.

A treatment-related AE is defined as an AE as being related to the study drug. If an AE has missing relationship it is assumed to be related to the study drug for analysis purposes.

Maximum severity will be assumed for an AE with missing severity.

The following tables will be presented for AEs:

- Summary of All Adverse Events, incidence and the number of events.
- Pre-therapy AEs by system organ class and preferred term, incidence and number of events
- TEAEs by system organ class and preferred term, incidence and number of events
- Treatment-related TEAEs by system organ class and preferred term, incidence and number of events

- Serious TEAEs by system organ class and preferred term, incidence and number of events
- TEAEs leading to treatment withdrawal by system organ class and preferred term, incidence and number of events
- All AEs of special interest by system organ class and preferred term, incidence and number of events
- TEAEs by system organ class, preferred term and maximum severity, incidence
- Treatment related TEAEs by system organ class, preferred term and maximum severity, incidence
- TEAEs by system organ class, preferred term and study drug relationship, incidence
- Listing of Deaths (presented in the Table section of the appendices)
- Listing of Serious TEAEs (presented in the Table section of the appendices)

All AEs will be listed.

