### 3 ENDPOINTS

#### 3.1 Primary Endpoint

- Comparison of adverse event (AE, SAE, AESI) frequency and severity by dose (cohort), for single and multiple administration, and by mutated gene (subcohort) and overall using the Safety Analysis Set following 12 weeks of MAD treatment and after 24 weeks of MAD treatment (12 weeks in the MAD part + 12 weeks in the MAD extension part; Week 25 visit) or discontinued earlier.

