### 6.2.7 Exposure to Study Drug

Exposure to study drug will be calculated separately for SAD and MAD + MAD Extension parts.

**SAD part:** exposure will be set to 1 if subject was dosed.

**MAD + MAD Extension part:** date of last MAD dosing - date of first MAD dosing + 1.

The exposure calculation will not take into account breaks in therapy.

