### **6.10 Exposure to Study Drug**

Extent of exposure (number of days of exposure to study drug) will be presented by treatment group (cohort, subcohort) for the Safety Analysis Set and separately for SAD and MAD parts.

Additionally, number of doses will be summarized.

All dosing information will be listed.

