## **8 PRIMARY AND FINAL ANALYSIS**

The study was terminated early and therefore planned primary and final analyses will not be performed. Reporting will include only same set of outputs as was delivered for the IDMC meetings (full safety analyses) and selected key efficacy endpoints. Section 12 of this SAP is updated to highlight which outputs are excluded from the planned.

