## 12 LIST OF TABLES, FIGURES AND LISTINGS FOR THE IDMC, PRIMARY ANALYSIS AND FINAL ANALYSIS

The following table includes details of the tables, figures and listings to be included within each section of the eCTD. The eCTD section is shown in bold. The following validation methods may be used:

- Independent programming of numbers and manual review of format (IP)
- Independent programming by statistician of numbers and manual review of format (Stat IP)
- Manual review (MR)
- Code review (CR)

Note: Strikethrough tables are ones that were originally planned for primary and final analysis but will be excluded from the abbreviated CSR because of the termination of the study.

Table Number	Table Title	Included in IDMC meetings	Validation Method	Shell Number (if repeat)
Items in bold are not table titles but references to the section headings within eCTD.				
14.1	Demographic Data			
14.1.1.1	Subject Enrollment – Screened Set	1-4	IP	
14.1.1.2	Screen Failures – Screened Set	1-4	IP	
14.1.1.3	Inclusion/Exclusion Criteria – Screened Set	1-4	IP	
14.1.1.4	Analysis Sets – Pre-Screened Set	1-4	IP	
14.1.1.5	Cumulative proportion of information – Safety Analysis Set	1-4	IP	
14.1.1.6	Subject Disposition – Safety Analysis Set	1-4	IP	
14.1.1.7	Subject Disposition by Country – Safety Analysis Set	1-4	IP	14.1.1.6
<del>14.1.1.8</del>	<del>Visits/Assessments Affected by COVID-19 – Safety Analysis Set</del>		<del>IP</del>	
14.1.2.1	Demographics – Safety Analysis Set	1-4	IP	
14.1.3.1	Medical History Related to Centronuclear Myopathy (CNM) – Safety Analysis Set	1-4	IP	
14.1.3.2	Medical History Unrelated to Centronuclear Myopathy (CNM) – Safety Analysis Set	1-4	IP	14.1.3.1
14.1.4.1	Prior Medications – Safety Analysis Set	1-4	IP	
14.1.4.2	Concomitant Medications – Safety Analysis Set	1-4	IP	14.1.4.1
14.1.5.1	Treatment Exposure – Safety Analysis Set	1-4	IP	
14.1.5.2	Treatment Compliance – Safety Analysis Set	1-4	IP	
14.2	Pharmacodynamics and Exploratory Efficacy			

Table Number	Table Title	Included in IDMC meetings	Validation Method	Shell Number (if repeat)
14.2.1.1	PROMIS Questionnaire, Descriptive Statistics – Pharmacokinetic Set		IP	
14.2.2.1	CGI I Questionnaire, Frequency Table – Pharmacokinetic Set		IP	
14.2.2.2	CGI I Questionnaire, Responders – Pharmacokinetic Set		IP	14.2.2.1
14.2.3.1	PGI-C Questionnaire, Frequency Table – Pharmacokinetic Set		IP	14.2.2.1
14.2.3.2	PGI-C Questionnaire, Responders – Pharmacokinetic Set		IP	14.2.2.1

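### The by-dose adverse event tables for the MAD part give crude counts over unequal follow-up, with no 12-week window, no stated Week 24 cap and no time at risk

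*SAP*

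**What the plan says.** - **Endpoint.** SAP 3.1 and Protocol 3.3.1 define the primary endpoint as AE frequency and severity compared by dose "following 12 weeks of MAD treatment and after 24 weeks of MAD treatment", or at earlier discontinuation.
- **Analysis.** SAP 6.14.1 states: "Adverse events will be reported separately for SAD and MAD + MAD Extension parts". An AE is treatment-emergent if it has "onset on or after the first dose of study drug and before last dose of study drug + 28 days". The listed tables give incidence and number of events. No AE table title in SAP 12 carries a 12-week cut, a 24-week cut or a time denominator.
- **Cohort timing.** Under Protocol 3.1.1, MAD2 opens after review of 6-week MAD1 data, and MAD3 after review of 12-week data from MAD1 and MAD2. Protocol 5.2 keeps everyone on weekly dosing until the last MAD3 subject has reached Week 25.
- **Follow-up information.** SAP 6.2.7 computes MAD exposure as "date of last MAD dosing - date of first MAD dosing + 1" and adds: "The exposure calculation will not take into account breaks in therapy". SAP 6.10 also summarises the number of doses, and SAP 6.4 the number of subjects completing each visit. None of these is related to the AE counts.
- **After termination.** SAP 7 says the study stopped before the interim analysis. SAP 8 drops the planned primary and final analyses but keeps the full safety outputs. The AE tables are therefore still produced.

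**The concern.** A crude count depends on how long each subject is observed. Here the end of the window follows each subject's own last dose, and the start follows the order in which cohorts opened. Time at risk is therefore tied to dose: whoever started MAD earlier, at the lower dose, tends to contribute more of it. If dose had no effect on AEs, the tables would still tend to show more events at the lower dose, and a real increase with dose would be partly masked. In a first-in-human dose comparison that is the unhelpful direction, and it touches the primary endpoint.

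**Working it through.** The plan gives no AE rate or power figure to reproduce; the sample size is explicitly not power-based. The check is how far follow-up differs by dose, and what that does to crude counts when the hazard is the same at every dose.

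**1. Minimum windows under the plan before termination (no review or enrolment lag, subjects still on drug).**
- MAD1 subjects whose Week 6 data open MAD2: 6 + 12 + 24 = 42 weeks.
- Other MAD1 subjects and all MAD2 subjects: 12 + 24 = 36 weeks, because the fourth IDMC review waits for the last subject of both cohorts to reach Week 13 (SAP 9).
- MAD3: 24 weeks.
- Adding the 28-day (4-week) tail: 46 or 40 weeks (MAD1), 40 (MAD2), 28 (MAD3).
- Event ratios against MAD3: 40/28 = 1.43 and 46/28 = 1.64. Counting the Week 6 visit as 5 weeks after first dose changes the latter to 45/28 = 1.61.

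**2. Which comparison survives termination.** The planned interim trigger was all Cohort 1 and 2 subjects completing 12 weeks of MAD or discontinuing (Protocol 9.2). MAD3 needed 12-week data from MAD1 and MAD2. Stopping before the interim analysis makes it probable, though not certain, that MAD3 never opened. MAD1 versus MAD2 is then the comparison in the report.

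**3. MAD1 versus MAD2 event ratio.** The documents give no dates, so these are assumptions: MAD2 had T weeks on drug at a common stop; k of 6 MAD1 subjects had a 6-week lead and the rest none; the hazard is constant and equal. SAP 9 asks for at least two subjects per sub-cohort past Week 6, so k = 2 fits one sub-cohort, k = 4 fits two, and k = 6 is everyone.

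Ratio = [k(T + 10) + (6 − k)(T + 4)] / [6(T + 4)]

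| T | k = 2 | k = 4 | k = 6 |
|---|---|---|---|
| 6 weeks | 72/60 = 1.20 | 84/60 = 1.40 | 96/60 = 1.60 |
| 12 weeks | 108/96 = 1.13 | 120/96 = 1.25 | 132/96 = 1.38 |

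With a 5-week lead, the k = 6 values are 15/10 = 1.50 and 21/16 = 1.31. A Week 24 cap changes nothing here, since MAD1 has at most 12 + 6 = 18 weeks on drug.

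**4. Subjects with an event.** Incidence = 1 − (1 − p)^(window/12), with an assumed 12-week risk p = 0.30 and T = 12. MAD2: 1 − 0.7^(16/12) = 0.378. MAD1 subjects with the lead: 1 − 0.7^(22/12) = 0.480. Averaged over MAD1: 0.412, 0.446 and 0.480 for k = 2, 4 and 6. The excess over MAD2 is 0.20, 0.41 and 0.61 of one subject in six.

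**5. Does the exposure table repair it?** Reported exposure omits the tail. Dividing counts by it at equal hazard (k = 6) gives MAD2/MAD1 = (10/6)/(16/12) = 1.25 at T = 6 and (16/12)/(22/18) = 1.09 at T = 12, so it overcorrects. Dividing by the full time at risk gives 1.00.

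**6. Does a Week 13 window repair it?** Not if it is cut at termination. At T = 6, k = 6 it compares 12 with 6 weeks, a ratio of 2.0, against 1.60 for the crude counts. If the tail is kept it is 12/10 = 1.20. A 6-week window reached by both cohorts gives 1.00.

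**7. Limit of the rate.** If all AEs fell in the first 4 weeks at equal risk, events per week at risk would be 1.60 (T = 6) or 1.38 (T = 12) times higher in MAD2 (k = 6). A common window would show 1.00.

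**The case against.** - **The extension is described as 12 weeks, so a Week 24 limit is implied.** This is a fair reading of SAP 1. SAP 6.14.1 does not say so, however. SAP 6.2.7 runs to the last MAD dosing, and Protocol 9.1 says later data are tabulated. Even with a cap, the 12-week comparison is missing.
- **The endpoint wording only sets when tables are run, and the loss of the primary and final analyses is disclosed.** True of SAP 8. The AE tables survive, though, and subjects dosed earlier still contribute more time.
- **Readers can already see follow-up.** This partly stands. Exposure days, number of doses, visit completion, disposition and a full AE listing are all kept. A reader might infer that the whole exposure summary ignores interruptions. Only the exposure-days calculation does: the SAP amendment log says the dose count was added because of many interruptions. What is missing is any link between these figures and the AE counts.
- **The effect is small and rests on assumptions.** This stands as a limit on size. T, k, p and a constant hazard are all assumed, and AEs clustered early would produce little crude imbalance.
- **Pre-dose AEs that ease after dosing might be counted as treatment-emergent.** A reader might infer this because a severity change opens a new record (Protocol 7.5.1). The documents do not support it well: the second part of the SAP definition covers pre-existing AEs and requires worsening.

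**Conclusion.** The point holds and should be fixed. As written, the MAD safety tables do not deliver the 12- and 24-week comparison that defines the primary endpoint, and their crude counts cover follow-up that tends to be longer at the lower dose. With equal hazards the higher dose tends to look safer.

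A reader might take 1.43 to 1.64 as the distortion in the final report. The documents do not support that: those ratios belong to a MAD3 comparison that probably will not be reported. For MAD1 versus MAD2 the illustrative event ratios are 1.20 to 1.60 (6 weeks) and 1.13 to 1.38 (12 weeks), on assumed follow-up times and a constant hazard. For subjects with an AE, the 12-week, 30%-risk example stays under one subject in six. Nor do the documents support reading this as an error-rate problem. No hypothesis is tested, so only the reading of the tables is affected. Confidence is medium, because actual follow-up by cohort is not given.

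**What to change.** In SAP 6.14.1 and the retained tables of SAP 12:

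1. In the overall AE summary for the MAD part, show by dose received the subject-weeks at risk (first MAD dose to the end of the treatment-emergent window, including the 28-day tail) and events per subject-week, beside crude incidence. Note that a rate assumes a roughly constant hazard.
2. Tabulate treatment-emergent AEs with onset from first MAD dose to the Week 13 visit, and to the Week 25 visit where reached, with later ones shown separately.
3. Where termination stopped subjects before Week 13, give the number who completed the window. Rely on the rate, or on a shorter window that all compared cohorts reached.

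As minor clarifications only: align the Protocol Figure 1 note, which puts data after Week 24 outside the statistical analysis, with Protocol 6.1.3.4 and 9.1, which tabulate and list those data but do not model them. Also state which part's first and last dose define the SAD and MAD windows, so that AEs between the parts are handled alike whether or not a subject continues.

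The cost is SAP wording, some programming and a few extra columns or tables, all from dates already collected. The abbreviated report becomes slightly longer.

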- The trial will start with the enrollment of approximately 6 subjects in Cohort SAD1.
- Cohort SAD2 can start after a favorable IDMC review of the 2-week safety and PK data of SAD1 (IDMC1).
- Cohorts SAD3 and MAD1 can start after a favorable IDMC review of the 2-week safety and PK data of SAD2 (IDMC2).
- Cohort MAD2 can start after a favorable IDMC review of the 2-week safety and PK data of SAD3, if available, as well as the 6-week safety and PK data of MAD1 (IDMC3).
- Cohort MAD3 can start after a favorable review of the 12-week safety and PK data of MAD1 and MAD2 as well as the MAD1 and MAD2 12-week PK and muscle biopsy data (IDMC4). In this meeting the IDMC will also recommend a starting dose for the pediatric DYN101-C102 study.

Details of the IDMC review will be described in the IDMC charter (see Section 9.12).

IDMC1: review of 2-week safety and PK data of SAD1; IDMC2: review of 2-week safety and PK data of SAD2; IDMC3: review of 2-week safety and PK data of SAD3, if available, and 6-week safety and PK data of MAD1; IDMC4: review of 12-week safety and PK data of MAD1 and MAD2, and 12-week PK and muscle biopsy data of MAD1 and MAD2.

Figure 2: Trial Cohorts and IDMC Reviews

Safety and tolerability will be evaluated throughout the trial from signing of the main ICF onwards until the last trial visit (i.e. EoT follow-up visit 3 months after the last IMP

administration). Safety evaluations will include monitoring of SAEs/AEs, clinical laboratory tests, ECGs, vital signs, and physical examinations at specified time points.

All enrolled subjects will undergo blood sampling for PK evaluations at specified time points. In addition, blood and/or urine samples will be collected for analysis of ADA and metabolic profiling.

PD/exploratory efficacy parameters including respiratory function, muscle strength and function, and dysphagia will be assessed, and a muscle biopsy will be taken at specified time points.

For subjects who provided a separate informed consent, blood samples will be collected for further exploratory research on blood biomarkers (including DNA). Participation in this part of the trial is optional and does not impact the subject's eligibility for participation in the trial. Subjects may continue to participate in the trial if they refuse to provide a sample or if they withdraw their samples.

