6.1.3.2 Single Ascending Dose Part

Subjects will receive a single IV administration of DYN101 on Day 1, after which they are followed for 4 weeks up to Day 29.

There will be a subsequent washout period of at least 12 weeks: during Weeks 5-17, subjects will be asked to visit the site every 2 weeks for safety follow-up, even if they do not continue to the MAD part. Where possible, the visits will take place on the same day of the week as the visit on Day 1.

Due to restrictions imposed in response to a pandemic that restrict subject visits, please contact the medical monitor to determine the strategy for continuing the subject in the trial. All efforts must be employed to maintain subject safety. Assessments, if feasible, must be collected during a phone call with the subject. The site should arrange the collection of the blood and urine samples, if at all possible.

Every 2 weeks following the Week 17 visit, subjects will be contacted by phone by qualified site personnel to follow-up on concomitant medications and AEs, until their assigned MAD cohort has been opened.

Subjects who participated in the SAD part will subsequently participate in the MAD part (provided the IDMC has given a favorable advice to proceed, see Section 3.1.1).

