### **6.2.6 Conventions for Missing and Partial Dates**

It is not expected that there will be any missing dates, however in the rare case that an AE start date or time is missing and it is unclear whether the AE is treatment emergent or not then a conservative approach will be taken and it will be assumed that the AE occurred after first dosing (earliest date of all doses during the whole study).

Partial or missing stop date will be imputed as follows:

If the stop date is completely missing and the event has resolved, or the subject has stopped taking the concomitant medication, the stop date will be imputed as the date of the subject's end of study visit

- If only the year is known, the stop date will be imputed as "31-Dec" of that year or as the date of the subject's last clinic visit in the study if in the same year.
- If the month and year are known, the stop date will be imputed as the last day of that month unless the stop date corresponds to the same month as the subject's last clinic visit in which case the date of subject's last clinic visit in the study will be used instead.

Missing start date will be imputed as follows:

- If the stop date occurs on or after the start of study drug or the event / concomitant medication is ongoing, the start date will be imputed as the date of the first dose of study drug.
- If the stop date occurs before the start of study drug, the start date of the event / concomitant medication will be imputed as the subject's screening date or the stop date of the event / concomitant medication whichever the earlier.

Partial start date (year present, but month and day missing) will be imputed as follows:

- If the stop date occurs on or after the start of study drug or the event / concomitant medication is ongoing, and the year is the same as the year of first dosing the start date will be imputed as "01-Jan" of the same year or the date of the first dose of study drug whichever is latest. If the year is different from the year of first dosing "01-Jan" will be used.
- If the stop date occurs before the start of study drug, the start date of the event / concomitant medication will be imputed as the "01-Jan" of the same year.

Partial start date (month and year present, but day missing) will be imputed as follows:

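### SAP 6.14.1 gives one TEAE window but tabulates SAD and MAD separately, so single-dose TEAE time depends on whether and when a subject went on to MAD

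*SAP*

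**What the plan says.** SAP 6.14.1 opens with "Adverse events will be reported separately for SAD and MAD + MAD Extension parts". Its TEAE definition then gives one window for all parts. An AE qualifies if it has "onset on or after the first dose of study drug and before last dose of study drug + 28 days", and a pre-existing AE qualifies if it worsens in that window. Neither dose is tied to a part, and nothing says which table takes an AE that starts between the single dose and the first MAD dose. Nearby sections anchor on the trial as a whole. SAP 6.2.6 explains first dosing as "earliest date of all doses during the whole study", and SAP 6.2.3 and 6.2.5 count baseline and study day from the first SAD dose.

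Protocol 6.1.3.2 describes the whole wait under the SAD part. Subjects receive one infusion on Day 1, "after which they are followed for 4 weeks up to Day 29". The text continues: "There will be a subsequent washout period of at least 12 weeks", with visits every 2 weeks to Week 17 "even if they do not continue to the MAD part". After that come phone calls every 2 weeks "to follow-up on concomitant medications and AEs, until their assigned MAD cohort has been opened". AEs are therefore collected throughout the wait.

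The primary endpoint (SAP 3.1) compares AE frequency and severity by dose, for single and for multiple administration. SAP 6.2.7 sets SAD exposure to 1 for every dosed subject.

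**The concern.** A SAD incidence table by dose is readable only if subjects are counted over comparable time. Here that time appears to depend on events unrelated to the single dose: whether the subject went on to MAD, and how soon the assigned MAD cohort opened. A cohort could then show more or fewer single-dose TEAEs with no difference in drug effect, and subjects who stopped after SAD would look safer because their count closes early. With SAD exposure fixed at 1, the planned outputs offer no time denominator to reveal or correct this.

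Early termination does not remove the issue. SAP Section 8 keeps the full safety analyses, and Section 12 keeps the TEAE tables in the abbreviated report.

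**Working it through.** 1. **The plan's own figure.** Follow-up of 4 weeks plus washout of at least 12 weeks gives 4 + 12 = 16 weeks, or Day 16 × 7 + 1 = 113. This matches SAD Week 17 (Day 113, +16 weeks) in the SAD follow-up schedule.

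2. **Plain reading: last dose means last dose in the trial.**
   - Subject who continues to MAD: every AE from the SAD dose to the first MAD dose is a TEAE. No MAD dose has yet been given and the Protocol places the wait under SAD, so the SAD table is its natural place. SAD TEAE time is at least 16 weeks, and longer if the MAD cohort opens late.
   - Subject with no MAD dose: the last dose is Day 1, and onset must fall before Day 1 + 28 = Day 29. SAD TEAE time is 28 days, or 4 weeks.
   - Ratio: at least 16 / 4 = 4. Both subjects are asked to attend to Week 17, so 16 − 4 = 12 weeks of the same collected follow-up counts for one and not for the other.

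3. **Per-part reading: last dose means last dose in the part.** SAD TEAE time is then 4 weeks for everyone, so the windows are equal. But an AE with onset from Day 29 to the first MAD dose is a TEAE in neither part. That is at least 12 of the 16 weeks, or 75% of the shortest possible interval.

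4. **Size on the plain reading.** The documents give no background AE rate, so r below is an assumption, equal in all subjects and constant over time, with no drug effect. P(at least one SAD TEAE) = 1 − exp(−r × weeks).

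| r per week | 4-week window | 16-week window |
|---|---|---|
| 0.02 | 1 − exp(−0.08) = 8% | 1 − exp(−0.32) = 27% |
| 0.05 | 1 − exp(−0.20) = 18% | 1 − exp(−0.80) = 55% |

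The right-hand column is a floor, because the wait may exceed 16 weeks. In six subjects the expected numbers with a SAD TEAE are about 0.5 against 1.6 at the lower rate, and 1.1 against 3.3 at the higher.

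**The case against.** **The text allows a per-part reading.** This stands. SAP 6.14.1 does not say whole study for the last dose; that phrase is attached only to first dosing in 6.2.6. Nor does it say that events in the wait go to the SAD tables. But the second reading exchanges unequal windows for lost events, so a rule is still needed.

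**The trial is descriptive.** Protocol 2.4 plans no hypothesis test. All AEs are listed, study day runs from the first SAD dose, and the table of AEs of special interest is not limited to TEAEs. A careful reader could therefore rebuild onset times. This limits the harm, but the by-dose incidence tables are the primary endpoint's output. The treatment-related tables and the serious-event listing in the table section are themselves restricted to TEAEs. A shift of one or two subjects matters with about six per dose.

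**Day 113 is a choice.** It is, but it has a reason. It is the protocol's end of washout. With the 21-day terminal half-life in monkeys (Protocol 1.3.1), about 0.5^(28/21) = 40% remains at Day 28 and 0.5^(112/21) = 2.5% at Day 112.

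**A stronger inference: the wait grows with dose.** A reader might infer this from the IDMC gates, since "Cohort MAD3 can start after a favorable review of the 12-week safety and PK data of MAD1 and MAD2". The gates do not force it, because they say when a cohort can start, not when it must. Setting aside the 7-day sentinel interval and review time, consider SAD1 at week 0, SAD2 at 6, SAD3 at 18, MAD1 at 16, MAD2 at 22 and MAD3 at 34. Every gate is met, and the waits are 16 − 0, 22 − 6 and 34 − 18: 16 weeks in all three cohorts. SAD3 data are required at the third data review only if available. Slow SAD enrolment can reverse the order. Take 20 weeks from first to last subject dosed in a SAD cohort, 1 week in a MAD cohort and a 2-week IDMC lag (all assumed). SAD cohorts then start at weeks 0, 24 and 48 and MAD cohorts at 48, 60 and 84. The mean waits are 48, 36 and 36 less (20 − 1)/2, or 38.5, 26.5 and 26.5 weeks. The MAD dose may also differ from the SAD dose.

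**Conclusion.** The concern holds as a defect in the TEAE rule. On the plain reading, SAD TEAE incidence by dose is confounded with whether and when MAD began: 28 days of counted time against at least 16 weeks. On the per-part reading the windows are equal, but AEs from about Day 29 to the first MAD dose drop out of all TEAE tables.

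The contrast of 4 with at least 16 weeks comes from the documents and needs no enrolment assumption. The percentages rest on the assumed background rates.

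No direction by dose can be claimed. It depends on enrolment speed, on the MAD cohort assigned, and on whether MAD3 opened. SAP Section 7 says the trial ended before the interim analysis, whose planned trigger (cohorts 1 and 2 through 12 weeks of MAD) closely matches the gate to MAD3. MAD3 therefore probably never opened, though this is an inference. A SAD3 subject with no MAD dose would then have the shortest window, and later events at the highest single dose would be under-counted.

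**What to change.** In SAP 6.14.1, define first and last dose by part and state where each AE is tabulated:

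- **SAD TEAE:** onset or worsening from the SAD dose to Day 113 or the first MAD dose, whichever is first. Apply this to all SAD subjects, whether or not they continue. Show Day 1-29 and Day 30-113 separately.
- **Between parts:** AEs from Day 114 to the first MAD dose in their own column by SAD cohort, not counted in SAD TEAE incidence.
- **MAD TEAE:** onset or worsening from the first MAD dose, keeping the existing end rule relative to the last MAD dose.

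The cost is SAP wording and a change to the AE flag derivation, with no new data. Compared with the plain reading, SAD TEAE counts fall for subjects who waited beyond Day 113 and may rise for those who had only the single dose.
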